10 DEVICE MALFUNCTIONS

A device malfunction means the failure of the device to meet its performance specification or otherwise perform as intended. Any defective lens that is *likely* to cause or contribute to a *Serious Adverse Event* should be reported to CORE and the sponsor **within 24 hours** of the investigator becoming aware of the malfunction. The Ethics Board would also be notified within 24 hours of any device malfunction that may contribute to a *Serious Adverse Event*.

Other defective lenses should be reported to CORE as soon as possible (usually in weekly study updates).

This clinical study will also ascertain satisfaction or preference with subjective attributes such as comfort, vision, or lens handling. Responses to these subjective questionnaires will not be considered as complaints or device malfunctions.

11 STUDY COMPLETION AND REMUNERATION

At the last scheduled protocol visit a study completion form will be completed, which requires the signatures of both the participant and the investigator. Participants will also be provided with a letter of appreciation.

Once their involvement in the study is complete, participants will be informed about receiving feedback following study completion in the Letter of Appreciation.

Participant remuneration will be paid as per site contract.

12 STATISTICAL ANALYSIS AND DATA MANAGEMENT

12.1 STATISTICAL ANALYSIS

All data will be analyzed by CORE at the University of Waterloo. Descriptive statistics will be provided on information regarding demographics (e.g. age, sex).

Differences between lenses and differences over time will be compared using either Paired t-tests or Wilcoxon matched pairs. Analysis will be conducted using Statistica 13 and SPSS 27.0. The appropriate tests will be selected based on tests of normality - non-parametric tests will be used for data not showing a normal distribution. Means and standard deviations will be provided for each variable. Medians will be provided for those variables analyzed with non-parametric tests. For all tests, values of p<0.05 will be considered significant.

For assessments conducted for each eye separately, the right eye will be used for analysis. If a general difference is found (paired t-test / Wilcoxon matched pairs) between OD and OS, a comment will be provided. Visual acuity data will be analyzed using OU.

For the agreement and preference data, binomial testing will be used to analyze the count data of subjective answers: For agreement analysis, "strongly agree" and "agree" will be combined into a single "agreement" category; similarly, "strongly disagree" and "disagree" will be combined into a single "disagreement" category. The number of "neither agree/disagree" ratings will be evenly distributed to these two categories on the basis they would be equally likely to choose either. Comments regarding the clinical relevance of differences in subjective ratings will be based on the conclusion by Navascues-Cornago et al.³ that on a scale of 0-100, differences greater or equal to 7 points would generally represent a difference that a patient would notice.

Equivalence testing will be conducted for ratings of comfort, dryness, vision clarity and overall satisfaction. Testing will be performed using Mintab 21.4. A value of 7 will be used as the margin for equivalence³.

Equivalence testing of visual acuity will be conducted using an equivalence margin of 0.10 logMAR.⁴⁻⁶

Additional analysis will determine the number of lenses and fit attempts needed to determine the optimal lens prescription.

Table 6: Statistical procedures

Variable	Analysis	Statistical test
Ratings: Likert & Preference	Comparison between study days	Freidman ANOVA
	and/or between contact lenses per	Wilcoxon matched pairs test
	time point.	Equivalence testing using +/- 7 units as
		the margin; on a small sub-set of
		numerical ratings only,
	Comparison between study days	Freidman ANOVA
	and/or between contact lenses per	Wilcoxon matched pairs test
	time point.	RMANOVA
Demographics	Descriptive stats	One or more: mean, median*, mode,
Lens fit variables		standard deviation, minimum, maximum,
		frequency count

^{*} For non-parametric data only

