3 OBJECTIVES

The objective of the study is to compare the lens performance of CONTROL and TEST.

The primary outcome variable for this study is:

 'Lens handling for insertion', using a 0-100 scale, collected in office after 1 month of study lens wear.

Also of interest are subjective feedback on comfort, vision and overall performance using ratings, agreement questions and preferences.

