5 MATERIALS AND METHODS

5.1 STUDY DESIGN

5.1.1 OVERALL DESIGN

This is a prospective, randomized, participant-masked, crossover, bilateral dispensing study conducted at approximately 5 clinical practice sites in the United States and Canada. Each lens type will be worn for approximately 4-6 weeks: the lens prescription of each lens type will be

optimized after 3-10 days wearing experience, prior to starting a 1-month (28-32 days) wear period.

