5.1.2 RANDOMIZATION

Participants will wear the CONTROL and TEST lenses in a randomized order.

A randomization schedule will be generated for each site using a web-based program (for example, www.randomization.com or similar). to determine the order CONTROL and TEST lens wear. The final study randomization schedule will be generated by CORE's Database Administrator and provided to each site.

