5.3 STUDY POPULATION

5.3.1 SAMPLE SIZE CALCULATION

The sample size was calculated using lens handling data from a previous study comparing Lens A against lens B (CooperVision, data on file). In that study a 0-100 scale was also used and a target difference of 5 units on the 0-100 scale was chosen as a meaningful clinical difference in 0-100 subjective responses.

Using the 0-100 scale data described above for 'lens handling for insertion', where the data showed a standard deviation of 12.7 and when applying requirements of 80% power and alpha 0.05 in a two-tailed t-test, a minimum sample size of 53 participants is recommended in order to detect a mean difference of 5 units.

To account for dropout, up to 60 participants may be randomized and dispensed with study product in total, with the target of at least 53 completing the study.

[figure not shown]

Figure 1: Sample size calculation graph

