5.3.3 INCLUSION AND EXCLUSION CRITERIA

A person is eligible for inclusion in the study if he/she:

- 1. Is at least 42 years of age and has full legal capacity to volunteer;
- 2. Has read and signed an information consent letter;
- 3. Self reports having a full eye examination in the previous two years;
- 4. Anticipates being able to wear the study lenses for at least 8 hours a day, 5 days a week;
- 5. Is willing and able to follow instructions and maintain the appointment schedule;
- 6. Habitually wears spherical multifocal soft contact lenses, for the past 3 months minimum[^];
 - Maximum of 4 participants (out of 12) per site may be habitual wearers of daily disposable lenses,
 - Maximum of 4 participants (out of 12) per site may be habitual wearers of Biofinity Multifocal.
 - Maximum of 4 participants (out of 12) per site may be habitual wearers of either TOTAL30 Multifocal or AirOptix plus HydraGlyde Multifocal
- 7. Has refractive astigmatism no higher than -0.75DC;
- 8. Is presbyopic and requires a reading addition of at least +0.75D and no more than +2.50D;
- 9. Can be fit and achieve binocular distance vision of at least 20/30 Snellen which participants also deem to be 'acceptable', with the available study lens parameters (Distance sphere +4 to -6; near addition as per study design).

^Exceptions may be permitted after discussion with the study monitor or sponsor to target the anticipated habitual lens distribution across all sites. If necessary, additional exceptions may be permitted after discussion with the study monitor or sponsor.

A person will be excluded from the study if he/she:

1. Is participating in any concurrent clinical or research trial;

- 2. Has any known active* ocular disease and/or infection that contraindicates contact lens wear:
- 3. Has a systemic condition that in the opinion of the investigator may affect a study outcome variable:
- 4. Is using any systemic or topical medications that in the opinion of the investigator may affect contact lens wear or a study outcome variable;
- 5. Has known sensitivity to the diagnostic sodium fluorescein used in the study;
- 6. Self-reports as pregnant, lactating or planning a pregnancy at the time of enrolment;
- 7. Has undergone refractive error surgery or intraocular surgery.

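### The lens order is randomised, but the lens comparison has no period term, so a period shift in the insertion rating would on average cost power and precision

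*Combined protocol and SAP*

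**What the plan says.** - **Design.** Section 5.1.2: "Participants will wear the CONTROL and TEST lenses in a randomized order". It continues: "A randomization schedule will be generated for each site using a web-based program". No order ratio or block size is given.
- **Primary outcome.** Section 3 names lens handling for insertion, "using a 0-100 scale, collected in office after 1 month of study lens wear". Each participant therefore gives one rating per lens, one in each period.
- **Analysis.** Section 12.1: "Differences between lenses and differences over time will be compared using either Paired t-tests or Wilcoxon matched pairs". Tests of normality decide between the two. No legible text names a period effect or a sequence effect.
- **Table 6.** It also lists Friedman ANOVA and RMANOVA. The row with RMANOVA has lost its variable label in the text available, and the comparisons that can be read there are between study days and between lenses. Nothing below rests on that row.
- **Sample size.** Section 5.3.1 starts from earlier lens-handling data, "where the data showed a standard deviation of 12.7 and when applying requirements of 80% power and alpha 0.05 in a two-tailed t-test", and a target difference of 5 units, which gives 53. It leaves a margin for losses: "up to 60 participants may be randomized and dispensed with study product in total, with the target of at least 53 completing the study".

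**The concern.** In a two-period crossover, ratings can differ between the first and second period for reasons unrelated to the lens, such as practice or a changed frame of reference. Call this shift P (period 2 minus period 1). With a true lens difference d, the within-participant differences centre on d + P in one order and on d - P in the other. A plain paired test pools the two groups and treats the gap between them as noise.

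Two things follow. The standard error is too large for the comparison that was designed, so power falls and the interval widens even with exactly balanced orders. If the orders are unequal among those analysed, the observed lens difference also moves by P × (n1 - n2)/n, in a direction nobody can know beforehand. Random order makes that movement average to zero over repeated trials, but it does not remove it from the one trial that is run.

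**Working it through.** **Inputs.** From section 5.3.1: SD 12.7, difference 5, two-sided alpha 0.05, 80% power, 53 completers, up to 60 randomised. Assumed, because the plan gives none: P = 3, 5 or 8 units.

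**The plan's own figure.** A paired t-test by noncentral t, with noncentrality 5 × √n / 12.7, gives power 0.795 at n = 52, 0.803 at n = 53 and 0.851 at n = 60. The stated 53 is reproduced, with 12.7 read as the SD of within-participant differences. Read as a per-group SD for two independent groups, it would need 102 per group.

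**Effect on the plain test.** The SD it uses becomes about √(12.7² + P²). The 95% CI half-width at n = 53 is 2.007 × √(12.7² + P²)/√53:
- P = 0: 3.50
- P = 3: 3.60
- P = 5: 3.76
- P = 8: 4.14

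**Period-adjusted analysis.** The estimate is (m1 + m2)/2, where m1 and m2 are the mean lens differences in the two orders, so P cancels. Its standard error is ½ × s × √(1/n1 + 1/n2), on n - 2 degrees of freedom, where s is the within-order SD. With s = 12.7, power is 0.803 at 27/26, 0.796 at 30/23 and 0.851 at 30/30, whatever P is.

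**Simulation.** 200,000 trials per setting, within-order SD 12.7, true difference 5. A range covers the two directions of the shift.

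| P | Plain power, 27/26 | Plain type I error, 27/26 | Plain power, 30/30 | Plain power, 30/23 | Estimate moves at 30/23, P × 7/53 |
|---|---|---|---|---|---|
| 3 | 77.9-79.6% | 4.4% | 83.9% | 71.8-84.5% | 0.40 |
| 5 | 74.3-77.6% | 3.6% | 81.4% | 63.0-85.9% | 0.66 |
| 8 | 65.6-71.6% | 2.1% | 75.2% | 46.1-86.1% | 1.06 |

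The adjusted analysis stayed at 80% (27/26), 85% (30/30) and just under 80% (30/23) throughout.

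- **Small shifts.** At 27/26, plain power is 79.6-80.4% for 1 unit and 78.9-80.1% for 2 units.
- **Completers for 80% power, plain test, balanced orders.** About 56 for P = 3, 58 to 60 for P = 5, and 67 to 68 for P = 8.
- **Order by simple randomisation, n = 53.** Plain power is 78.1%, 74.5% and 66.2% for 3, 5 and 8 units, against 79.4-79.5% adjusted. Average bias is within 0.01 unit and type I error is 4.9-5.1%.
- **Wilcoxon.** In a smaller simulation (20,000 trials, balanced), power is 78.7% with no shift, 75.4% at P = 5 and 61.7% at P = 10. Switching to the rank test gives no protection.

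**If 12.7 already contains the period variance.** The within-order SD is then √(12.7² - P²) = 12.34, 11.67 or 9.86. At 27/26, plain power is 80.0-81.7%, 80.8-83.6% and 83.3-88.3%; adjusted power is 82.5%, 86.4% and 95.1%.

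**The case against.** The strongest reply is that the harm depends on a quantity the plan never gives. Five units is the whole target difference, and 8 exceeds the 7 points that section 12.1 takes as noticeable to a patient. The design also argues against a large learning effect. Inclusion criterion 6 normally requires that the participant "Habitually wears spherical multifocal soft contact lenses, for the past 3 months minimum" (exceptions are possible), and each lens is "optimized after 3-10 days wearing experience, prior to starting a 1-month (28-32 days) wear period". At 3 units or less, with nearly balanced orders, the loss is at most about 2.5 points. That stands, and it limits how strongly the point can be put.

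The origin of 12.7 is also open. If it is a raw SD of differences from an earlier crossover, and a similar shift occurs here, the plain test keeps at least the planned power. That stands too: the loss is then only relative to a better test.

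The 30/23 ranges include gains as well as losses. They show sensitivity to one assumed imbalance, not an average loss, and section 5.1.2 does not let a reader judge how likely such a split is.

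Two replies do not dispose of the point. Randomised order removes average bias but not the added variance; the loss is present at exactly 30/30. The extra seven participants are there for dropout, and they absorb a 5-unit shift only if nearly all 60 complete. They do not absorb 8 units.

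**Conclusion.** The concern holds. The planned paired tests are valid on average for a randomised-order crossover, and near balance they are conservative when a shift exists. They are inefficient because they leave out a factor the design already randomises. The cost ranges from negligible at 1 to 2 units to roughly 8 to 14 points of power at 8 units (27/26, 53 completers).

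These figures assume normal differences, a within-order SD of 12.7, a true difference of 5 and the stated shifts. Confidence is moderate, because neither the shift nor the make-up of 12.7 can be settled from the documents. The case for changing the plan is that the protection is nearly free, not that a large shift is expected.

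**What to change.** In section 12.1, prespecify one primary analysis of the 1-month insertion rating that adjusts for period. This can be a linear mixed model with lens, period and sequence as fixed effects and participant as a random effect, or the equivalent period-adjusted crossover t analysis. Report the adjusted lens difference with its 95% CI. Keep a rank test on period-adjusted differences as a sensitivity analysis, and make Table 6 agree.

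Stating the order ratio and any blocking in section 5.1.2 would limit unequal orders. It does not replace the period term, since the loss remains at exact balance. Naming one primary test instead of choosing by normality is a separate prespecification gain.

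The cost is wording in section 12.1 and Table 6, and the model runs in the SPSS already named. It uses one degree of freedom. With no period shift, that is under 0.2 point of power when orders are balanced and about 0.7 point at 30/23 (80.3% to 79.6%).

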5.4.3 OTHER PRODUCTS

Sodium fluorescein will be used to assess corneal and conjunctival staining.

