7 POTENTIAL RISKS AND BENEFITS TO HUMAN PARTICIPANTS

There may be no direct benefits to the subjects in this study. Participation in a study may contribute to scientific research information that may be used in the development of new contact lens products. The subjects will receive an examination of the front part of their eyes and may have the opportunity to try a different type of soft contact lenses and/or different lens care products at no cost to them. The contact lens materials used in this study are commercially available as daily wear. This study will investigate participants' wearing schedule intended for daily wear (NOT extended wear), similar to the average wearing time of 10-16 hours for daily wear lenses.

All lenses used in this study are IDE exempt under 21 CFR 812.2(c)2.

The habitual lens and the two study contact lens types will be worn as per their approved use; on a daily wear, monthly-replacement basis. When contact lenses are worn on a daily wear basis there is a small risk of an adverse event compared to not wearing contact lenses. When contact lenses are worn on an extended wear basis, there is a significantly increased risk of an adverse reaction compared with wearing contact lenses on a daily wear basis.

Adverse events and/ or complications in daily wear of soft contact lenses can occur (e.g.: inflammation and infection). Complications that may occur during the wearing of contact lenses include discomfort, dryness, aching or itching eyes, excessive tearing, discharge, hyperemia and variable or blurred vision. More serious risks may include pain, photophobia, iritis, corneal edema or eye infection. Although contact lens-related infections are very infrequent, the possibility does exist. The incidence of infection due to day-wear soft lenses is 0.035%. Almost always an infection will occur only in one eye. This risk is assumed by 35-million Americans who currently wear contact lenses and only current soft lens wearers will be recruited for this study.

A dye (fluorescein) normally used for eye examinations is being used in this study. Although rare, it is possible to have an allergic reaction to the dye. Participants will be asked if they have a known allergy or sensitivity to fluorescein.

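### Right-eye-only analysis of per-eye assessments is valid, but it gives up some precision and leaves about half of one-sided findings below the adverse-event threshold out of the lens comparison

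*Combined protocol and SAP*

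**What the plan says.** Section 12.1 sets the rule: "For assessments conducted for each eye separately, the right eye will be used for analysis". The left eye has one stated use: "If a general difference is found (paired t-test / Wilcoxon matched pairs) between OD and OS, a comment will be provided". Visual acuity is exempt: "Visual acuity data will be analyzed using OU". No other section gives a both-eye analysis of variables assessed per eye.

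Other sections bear on what the rule covers:

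- Section 5.1.1 describes bilateral dispensing, so both eyes wear each study lens.
- Section 5.4.3: "Sodium fluorescein will be used to assess corneal and conjunctival staining".
- Section 5.6.3 defines lens fit as a four-level centration grade and a yes/no judgement of acceptability. It does not say whether these are recorded per eye.
- Table 6 in section 12.1 gives lens fit variables descriptive statistics only, including frequency counts.
- Sections 8.2 and 8.3 require a form for every adverse event, with one for each eye when both are involved, and put all events in the study report.

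**The concern.** Both eyes wear the lenses, and the right-versus-left comparison already requires left-eye data. Yet those data do not contribute to the comparison of the two lenses. Two things are at stake.

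The first is precision. For a per-eye variable that is tested between lenses, the second eye carries some extra information, and the plan does not use it.

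The second is completeness. A sign or a poor fit that occurs only in the left eye is absent from a right-eye table. The right-versus-left test does not repair this, because it looks for a systematic shift between eyes. One-sided findings that fall equally often on either side produce no average shift, so the test can be unremarkable while left-eye findings remain outside the lens comparison.

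**Working it through.** **The plan's own figure.** Section 5.3.1 gives a target difference of 5 units, "requirements of 80% power and alpha 0.05 in a two-tailed t-test" and "the data showed a standard deviation of 12.7". Taking 12.7 as the SD of the paired difference:

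- The normal approximation gives (12.7 × (1.960 + 0.842) / 5)² = 50.6.
- With the noncentral t distribution, power is 0.795 at n = 52 and 0.803 at n = 53.

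The stated 53 is reproduced. It concerns the 0-100 rating of handling for insertion, described as a single rating per participant, so the right-eye rule does not touch it.

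**Precision.** Let d_R and d_L be a participant's lens difference (TEST minus CONTROL) in the right and left eye, with common variance s² and correlation rho. Then

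- Var(right eye only) = s²
- Var(mean of both eyes) = s²(1 + rho)/2

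One eye therefore keeps (1 + rho)/2 of the two-eye information and loses (1 − rho)/2. With both eyes, 53 participants are worth 53 × 2/(1 + rho) right-eye participants, and confidence intervals shorten by 1 − √((1 + rho)/2). The documents give no rho, so a range is shown.

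| rho (assumed) | Information kept by one eye | Right-eye equivalent of 53 with both eyes | Interval shorter by |
|---|---|---|---|
| 0 | 50% | 106 | 29% |
| 0.5 | 75% | 70.7 | 13% |
| 0.8 | 90% | 58.9 | 5% |
| 0.9 | 95% | 55.8 | 2.5% |

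**One-sided findings.** If either side is equally likely, a right-eye dataset omits 1/2 of unilateral findings. With k such findings, the chance that none is in the right eye is 0.5^k: 50% for one, 25% for two, 12.5% for three.

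As a share of all participants with a finding in any eye, the omission is smaller because some findings are bilateral. Let p be the eye-level rate and c the between-eye correlation of the finding, both assumed:

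- P(both eyes) = p² + c·p(1 − p)
- P(one eye only) = 2(p − P(both eyes))
- Share omitted = ½ × P(one eye only) / (P(one eye only) + P(both eyes))

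For p = 0.05 and c = 0.5: P(both) = 0.0025 + 0.02375 = 0.02625, P(one only) = 0.0475, and the share omitted is ½ × 0.0475 / 0.07375 = 32%. The same formula gives 49% at c = 0, 16% at c = 0.8 and 9% at c = 0.9.

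**Which findings these are.** The adverse-event coding table in section 8 has thresholds. Corneal staining is coded from the dense coalescent level (code 14). Neovascularization (15) and papillary conjunctivitis (22) need a two-grade change from baseline. A milder left-eye sign that meets no other code is not an adverse event and also falls outside the right-eye analysis. The same holds for left-eye decentration or unacceptable fit, if fit is recorded per eye.

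**The case against.** The strongest reply is that one prespecified eye per participant is an accepted way to avoid treating two correlated eyes as independent. That stands: the rule creates neither bias nor excess type I error, and the alternatives improve on it rather than correct an error. Analysing the worse eye would also change what is estimated.

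Four further points stand in whole or in part.

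- **Lens fit is descriptive.** With no test planned, the variance argument does not apply to fit. Only the completeness argument does.
- **Ocular-health analysis is partly not visible.** Many procedure steps and one variable name in Table 6 are blacked out, and section 3 names no ocular-health outcome. Which slit-lamp grades are compared between lenses cannot be confirmed. Section 12.1 does show that some assessments are made per eye.
- **Important events are reported elsewhere.** Section 7 says "Almost always an infection will occur only in one eye". A reader might infer that half of infections would be missed. The documents do not support that: infectious keratitis and conjunctivitis are coded adverse events, and events in either eye are reported. The sentence shows only that findings can be one-sided.
- **The size depends on rho.** At a high between-eye correlation the gain in precision is small.

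None of this supplies a left-eye contribution to the lens comparison, or makes an average right-versus-left test sensitive to scattered one-sided findings.

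**Conclusion.** The point holds as a minor matter of efficiency and descriptive completeness. For a per-eye variable that is tested, the right-eye rule loses 25% of the two-eye information at rho 0.5 and 10% at rho 0.8. About half of one-sided findings below the adverse-event threshold stay out of the lens comparison. The first result assumes equal variance and the same lens effect in both eyes, and a value for rho. The second assumes that either side is equally likely.

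A reader might infer that half the fit and ocular-health data are discarded. Half the eye records are left out of the lens comparison, but the loss of information reaches half only at rho = 0, and the left eye is still used in the right-versus-left comparison. Nor do the documents support any effect on adverse-event reporting, the primary rating, visual acuity or the sample size of 53.

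**What to change.** Amend section 12.1 as follows.

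1. For graded per-eye variables that are tested between lenses, analyse the mean of the two eyes per participant, or fit a model with a participant effect.
2. Tabulate fit and ocular-health findings by lens for both eyes, or as the number of participants with the finding in any eye.
3. State whether lens fit, and the number of lenses and fit attempts, are counted per eye or per participant, so that it is clear what the rule covers.
4. Keep the right-eye analysis as a supportive result if continuity with earlier studies matters.

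No new data should be needed, because the planned right-versus-left comparison already requires left-eye values. The cost is a change of wording, a few extra tables and minor programming.

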16 REPORT

An interim analysis will be initiated when approximately 30 participants have completed, and results will be provided in PowerPoint format. The final analysis will be initiated when the last participant has exited the study and the final report will be prepared as Word document.

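### Splitting neutral agreement answers evenly before the binomial test makes that test generally conservative, and the loss grows steadily with the neutral share

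*Combined protocol and SAP*

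**What the plan says.** All of this is in the combined protocol and SAP.

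- Section 12.1, agreement and preference data: "binomial testing will be used to analyze the count data of subjective answers". For agreement items, the two agree levels are merged, as are the two disagree levels. Neutral "ratings will be evenly distributed to these two categories on the basis they would be equally likely to choose either".
- Section 12.1, significance level: "For all tests, values of p<0.05 will be considered significant".
- Section 3, status of these items: "Also of interest are subjective feedback on comfort, vision and overall performance using ratings, agreement questions and preferences". The primary outcome is the 0-100 score for lens handling on insertion.
- Section 5.3.1, numbers: "up to 60 participants may be randomized and dispensed with study product in total, with the target of at least 53 completing the study".
- Section 16: "An interim analysis will be initiated when approximately 30 participants have completed".

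Section 12.1 does not give the null proportion or the sidedness of the binomial test, whether it is exact or a normal approximation, what happens to an odd neutral count, or the neutral share expected. The even split is stated for agreement answers only.

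**The concern.** The stated reason for the split is that neutral respondents would be equally likely to go either way. Even if that is true, the calculation does not follow from it. People choosing at random would add binomial variation to the agree count, whereas allocating exactly half to each side adds none. The binomial test nevertheless computes its variance as if all n answers were independent draws. The agree-minus-disagree difference is unchanged while its assumed variance is inflated, so p-values are generally too large.

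At stake is whether agreement items are reported as significant. An item can miss p<0.05 because of the counting rule alone.

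**Working it through.** **Inputs.** From the documents: 53 target completers and at most 60 randomized (5.3.1), significance at 0.05 and the even split (12.1), and an interim look at about 30 completers (16). Assumed, because not stated: null proportion 50%, two-sided test, neutral share q from 5% to 30%, and 70:30 agree:disagree among non-neutral answers unless noted.

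**The plan's own figure.** The documents give no figure for the agreement analysis. The n of 53 comes from the primary outcome and reproduces: a paired t-test with SD 12.7, difference 5 and two-sided 0.05 has power 80.3% at n=53 and 79.5% at n=52.

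**Mechanism.** Let A, D and M be the agree, disagree and neutral counts, with n = A + D + M. After the split the agree count is A + M/2, and its distance from n/2 is (A − D)/2, whatever M is. Hence

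- split: z = (A − D)/√n
- neutrals excluded: z = (A − D)/√(A + D)

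The ratio of the two is √(1 − q).

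**Large-sample size**, 2·[1 − Φ(1.96/√(1 − q))]:

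- q = 10%: 1.96/√0.9 = 2.066, size 0.039
- q = 20%: 1.96/√0.8 = 2.191, size 0.028
- q = 30%: 1.96/√0.7 = 2.343, size 0.019

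Equivalently, a result whose correct p is 0.050 is printed as 2·[1 − Φ(1.96·√(1 − q))] = 0.063, 0.080 and 0.101.

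**Exact size and power at n=53.** These come from full enumeration over neutral and agree counts, with an odd neutral rounded up or down with equal weight.

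| Neutral | Size, excluded v split | Power at 70:30, excluded v split |
|---|---|---|
| 5% | 0.039 v 0.024 | 0.802 v 0.739 |
| 10% | 0.037 v 0.020 | 0.771 v 0.689 |
| 20% | 0.036 v 0.014 | 0.714 v 0.568 |
| 30% | 0.034 v 0.008 | 0.641 v 0.425 |

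**Other sample sizes.** Exact power loss (excluded minus split) at 70:30 over every n from 53 to 60:

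- 5% neutral: −0.015 to 0.063
- 10%: 0.000 to 0.082
- 20%: 0.04 to 0.15
- 30%: 0.10 to 0.22

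At 5-10% the exact loss depends on where the critical count falls. At n=58 it reverses at 5% (0.832 v 0.847) and vanishes at 10% (0.810 v 0.810). From 20% it is positive at every n in the range. A normal-approximation test is less affected by discreteness and loses 0.01 to 0.045 at 10%, 0.06 to 0.10 at 20% and 0.12 to 0.18 at 30%.

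**Interim, n of about 30.** Exact power is 0.424 v 0.388 at 20% neutral and 0.370 v 0.279 at 30%. It reverses at 5% (0.506 v 0.542) and 10% (0.473 v 0.493).

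**Single items at n=53.**

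- 27 agree, 13 disagree, 13 neutral. Normal approximation: 14/√40 gives p=0.027, and 14/√53 gives p=0.055. Exact: 0.038 excluded, 0.053 or 0.098 split, depending on where the odd neutral goes.
- 32/17/4 (7.5% neutral). Exact: 0.044 excluded, 0.053 split, with no rounding involved. The normal approximation is significant either way (0.032 v 0.039).

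**Exception on direction.** With an odd neutral count rounded to the larger side, an exact split p-value can be the smaller one. At n=58, 35/20/3 gives 0.058 excluded and 0.048 split. At n=30, 19/8/3 gives 0.052 and 0.043. No such change to significance was found at n=53.

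**The case against.** The case for leaving the rule alone has four parts.

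1. The size of the effect rests on inputs that the documents do not give. This stands. If opinion is one-sided, little is lost: at 80:20, n=53 and 20% neutral, power is 0.98 v 0.95.
2. Little rests on this test. Table 6 assigns Likert and preference ratings to Wilcoxon and Friedman procedures, which the split does not touch, and the primary outcome is a 0-100 score. This also stands and limits the severity.
3. The rule is disclosed, reasoned and errs toward caution. That is mostly true, but its reason does not justify its variance, and a test that runs well below its nominal level without saying so is not a deliberate safeguard.
4. Excluding neutrals changes the question to agreement among those with an opinion. For example, 23/10/20 gives p=0.035 although only 23/53 = 43% of respondents agreed. The limit on interpretation is real. The null that agree and disagree are equally likely is unchanged, however, and reporting the three counts makes the limit visible.

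A reader might also infer more than the documents support:

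- **That the rule produces false positives or threatens the main conclusion.** The computed type I error of the split test stays below 0.05, and the primary analysis does not use it.
- **That it matters only above some neutral share, such as 20%.** The documents set no cut-off and the large-sample loss is smooth; 32/17/4 changes verdict under the exact test at 7.5%.
- **That every p-value is too large.** The odd-count cases above show otherwise.

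**Conclusion.** The concern holds as a minor defect in section 12.1. The fixed even split makes the binomial test on agreement items generally conservative, because split answers enter n without adding variation. At n=53 and 70:30 the exact power loss is about 8 points at 10% neutral (0.771 − 0.689), 15 at 20% (0.714 − 0.568) and 22 at 30% (0.641 − 0.425).

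The mechanism follows from the text, given a test against 50%. The size depends on the assumed neutral share and agree:disagree split, two-sided testing and, at low neutral shares, the exact number of completers and the type of test. The documents cannot show whether any particular item will be affected.

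**What to change.** Replace the even-split sentence in section 12.1 with:

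*The p-value will come from a two-sided exact binomial (sign) test of agree v disagree among non-neutral answers against 50%; counts and percentages of agree, neither and disagree among all respondents will be reported beside it.*

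Describe the result as agreement among those expressing an opinion. If the even split is kept at all, keep it only as a descriptive or sensitivity analysis; a rounding rule for an odd neutral count is needed only there. Make the change before the interim analysis, so that the rule is not chosen after seeing data.

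The cost is one or two sentences and no new data. Fewer answers enter each test. Somewhat more items may reach p<0.05, and section 12.1 states no multiplicity control for them. The exact test among non-neutral answers nevertheless keeps its size per item below 0.05: 0.029 to 0.039 at every n and neutral share computed (n of 30, 51 and 53 to 60; 5% to 40% neutral).
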